7.2.2 Secondary Endpoints

Consistent with the secondary study objective to assess changes in metabolic response profile and markers of oxidative stress and inflammation the following endpoints will assessed:

- Improvement in metabolic response profile suggested by:
 - Change in metabolomics profile using liquid chromatography high-resolution mass spectroscopy (LC-MS). (Reference: Frediani JK. (2014) Plasma metabolomics in human pulmonary tuberculosis disease: a pilot study. PLoS ONE 9(10): e108854).
 - Lower levels of lactate, triglycerides.
 - Assessment of the integrated redox function (Reference: Jones DP. Measuring the poise of thiol/disulfide couples in vivo. Free Radical Biology and Medicine. 47(2009):1329-38.)
 - Plasma F2-isoprostanes will be measured by GC-MS as described by Roberts and Morrow; Plasma amino acids, metabolites and electrolytes. Plasma amino acid concentrations will be determined by reversed-phase HPLC after derivatization with phenylisothiocyanate
- Improvement in proteinuria (albuminuria).
- Assessment of nitrogen balance and anabolism with 24hr urine for urine creatinine, urine urea nitrogen.

7.3 Accrual, Follow-up, and Sample Size

The overall sample size for this project is 20. We anticipate recruiting 1-2 participants weekly for total study duration of 2 years.

Sample size was calculated based on values obtained from an estimated within individual coefficient of variation in values of ATP/O₂ ratio from MRS/OS of approximately 15% and values of test-retest reliability of pulse amplitude tonometry measures of vascular endothelial function from a recent published study. A total of 20 patients will enter this two-treatment crossover study. With this sample size, the probability is over 90% that we will detect a meaningful treatment difference of 20% for ATP/O2 ratio at a one-sided 0.05 significance level (Table 2). This is based on the assumption that the within-patient standard deviation of the response variable is 0.375 with a mean predicted ATP/O2 ratio of 2.5. Sample size was calculated using the following sample size calculator: http://hedwig.mgh.harvard.edu/sample_size/js/js_crossover_quant.html

	ATP/O ₂ ratio	
	Power	
Minimal detectable difference	80%	90%
20%	6	7
25%	4	5
33%	4	4
40%	3	4

Table 2. Samples size required to detect treatment effects for ATP/O2 ratio from MRS/OS and reactive hyperemia index (RHI) from PAT in crossover design.

7.4 Random Assignment / Study Arm Assignment

Investigational drug services will be responsible for randomization of participants into the two treatment groups.

7.5 Blinding

Study participants, investigators, and research coordinators will be blinded to the study. The investigational drug pharmacy will receive a receive treatment/placebo designation in a sealed envelope on the day of study drug/placebo initiation. Subjects will not be told of their assignment. Early unblinding will occur to protect patient safety in the event of an adverse event that the investigator believes may be relate to treatment.

7.6 Data Analysis

7.6.1 Primary Analyses

The major assumption in the cross-over trial is that there is no carryover effect of first period into the second period. The assumption is that a 3-week washout will be sufficient

to eliminate any potential carryover effect due to glutamine. The statistical model we assumed for continuous data from the 2×2 crossover trial:

Design	Period 1	Period 2
Sequence Placebo-Gln	A	В
Sequence Gln-Placebo	В	A

From this design we construct these differences for every patient and compare the two sequences with respect to these differences using a two-sample paired t test. Thus, we are testing:

$$H_0: \mu_{AB} - \mu_{BA} = 0$$

Where:
$$\mu_{AB} - \mu_{BA} = 2(\mu_A - \mu_B)$$

So testing
$$H_0: \mu_{AB} - \mu_{BA} = 0$$
, is equivalent to testing:

$$H_0: \mu_A - \mu_B = 0$$

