2.3 Study Design

Overview of study design

This is a placebo-controlled, double-blind crossover trial. There are 2 phases 14 days each separated by a 3-week washout period

A brief screening visit will assess eligibility criteria, and will include informed consent. Qualified participants will be stratified by diabetes status and randomly assigned (1:1) to 14 days of placebo followed by 14 days weeks of oral L-glutamine, or 14 days of oral L-glutamine followed by 14 days of placebo, each separated by a 3-week wash-out period.

Qualified participants will participate in 3 study visits, plus a screening visit. Study outcomes will be assessed at each of these 3 visits.

Subjects will receive 0.4 g/kg/day of L-glutamine in three divided daily doses. This dose was chosen based on a review of studies in the literature evaluating biological activity of glutamine on immune function and modulation of muscle turnover. Placebo will consist of identical appearing maltodextrin powder.

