4.3 Adherence Assessment

Adherence to the study treatment will be assessed by study coordinator phone call at day 7 of the study to assess adherence and inventory method to assess remaining medication/placebo at the end of the study. Adherence will be defined as consumption of at least 75% of the prescribed regimen. Up to 30 participants may be recruited to compensate for non-adherence or drop-out with the goal of 10 individuals completing in each treatment arm.

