5.0 STUDY PROCEDURES

Schedule of visits and procedures

An overview of the study visit and procedures schedule is presented in table 1. Presented below is additional information on visit-specific study procedures. Detailed instructions to guide and standardize all study procedures will be provided in the study-specific procedures manual.

Screening visit

Some components of the initial screening visit may be performed by telephone or in combination with other study visits in order to best accommodate participants' schedules. Once informed consent is obtained, the subject will undergo a baseline screening evaluation including an assessment of demographics, smoking history, medical history, medication inventory, with physical examination by study personnel. If the subjects meet the eligibility criteria the PI or Co-I will contact the subjects' primary physician regarding the subjects' involvement in the trial. The first study visit will be scheduled within 28 days of the screening visit. We will link to laboratory data from the CKD-MEND visit. The only lab tests that are not collected in CKD-MEND needed for this trial are metabolomics and redox proteome testing (see below).

Study drug dispensed at Visits 1 and 2

The participant will receive either placebo (maltodextrin powder) or glutamine from the Investigational Drug Service (IDS) and instructed on how to appropriately prepare it. He or she will be instructed to take the medication daily starting on the day after the study visit. They will be instructed to consume no protein for 30 minutes after glutamine or placebo consumption to prevent competitive binding for absorption with other amino acids.

Visit 1 – Visit 3

The participant will have been required to fast for 8 hrs prior to each visit and abstain from caffeine or smoking which can effect endothelial function for 8 hours prior to the visit. The following data will be obtained:

- vital signs,
- fasting blood collection,
- anthropometrics (height and weight),
- a urine pregnancy test will be given to women of child-bearing potential
- The MRS/OS and Muscle Fatigue tests will occur at the diagnostic imaging center at UWMC at visits 2 and 3. We will use the results of the MEND MRS/OS as the baseline for this study. Only 2 MRS/OS and Muscle Fatigue tests will be obtained per patient during this study because it will be assumed that there will be no carry-over effect of glutamine after the 3-week washout period.

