7.6.2 Secondary Analyses

We will test for difference in each marker of metabolic response profile, oxidative stress, and albuminuria in a similar fashion as above. Similar to above, we will use a two-sample paired t-test testing the difference in means comparing treatment to placebo.

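### Sections 7.6.1 and 7.6.2 call the test paired, but the printed hypothesis compares two independent sequences and needs an unpaired two-sample t-test on period differences

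*Combined protocol and SAP*

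**What the plan says.** Section 7.6.1 sets out a 2×2 crossover. Its table gives the placebo-first sequence as A then B and the glutamine-first sequence as B then A, so A is placebo and B is glutamine. It continues: "From this design we construct these differences for every patient". The order of subtraction is not given. The plan is then to "compare the two sequences with respect to these differences using a two-sample paired t test". The null hypothesis is μ_AB − μ_BA = 0, and the section states that μ_AB − μ_BA = 2(μ_A − μ_B).

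Section 7.6.2 says the secondary markers will be handled similarly: "we will use a two-sample paired t-test testing the difference in means comparing treatment to placebo".

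Two other places bear on the choice of test. Section 2.3 randomises patients 1:1 to sequence, stratified by diabetes status, and describes no matching of individuals. Section 5.0 states that "Only 2 MRS/OS and Muscle Fatigue tests will be obtained per patient during this study", at visits 2 and 3, so each patient supplies one post-treatment value per period and hence one difference.

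**The concern.** A two-sample test and a paired test are different procedures. The label joins them, and nothing else in the plan names the primary test. The contrast printed beside the label is between independent groups, so the named test does not match the stated hypothesis.

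The pairing in a crossover is used up when each patient's difference is formed. An analyst who takes *paired* at its word is most likely to pair each patient's glutamine value with the same patient's placebo value and test the mean of those differences. Section 7.6.2 invites this by speaking of comparing treatment to placebo. That test ignores period. The two imaging visits are on days 15 and 53, 38 days apart, and the documents neither give nor exclude a shift between them. At stake are the validity of the test if such a shift exists, and whether the choice of test is settled before the data are seen.

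**Working it through.** **1. Which test the identity requires.** Let D be period 1 minus period 2 for one patient, and let π₁ and π₂ be the period effects.
- Placebo-first: E(D) = μ_A − μ_B + (π₁ − π₂).
- Glutamine-first: E(D) = μ_B − μ_A + (π₁ − π₂).
- Difference between sequences: 2(μ_A − μ_B). The period effect cancels, and this is the printed identity.

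If D were instead glutamine minus placebo in every patient, the treatment effect would cancel in the comparison between sequences and only the period effect would remain. The identity therefore requires period differences compared between two independent groups. The matching test is unpaired, with N − 2 degrees of freedom.

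**2. The plan's own power figure.** Section 7.3 assumes that "the within-patient standard deviation of the response variable is 0.375 with a mean predicted ATP/O2 ratio of 2.5", and aims at a "meaningful treatment difference of 20% for ATP/O2 ratio at a one-sided 0.05 significance level" with 20 patients.
- Effect: 0.20 × 2.5 = 0.50.
- SD of a within-patient difference: 0.375 × √2 = 0.530.
- Standard error of the treatment estimate at 10:10: 0.530/√20 = 0.1186.
- Noncentrality: 0.50/0.1186 = 4.22.
- Unpaired test (18 df, critical t 1.734): power 99.2%.
- Within-patient test (19 df, critical t 1.729): power 99.2%.

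The claim of over 90% is reproduced under both tests.

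**3. If there is a period effect.** Let π be period 2 minus period 1, and let nP and nG be the completers in the placebo-first and glutamine-first sequences. For the within-patient test:
- The mean glutamine-minus-placebo difference has expectation effect + π(nP − nG)/N.
- The sum of squares is inflated, with noncentrality π²[N − (nP − nG)²/N]/0.530².

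For example, at 10:10 with π = 0.50 the bias is 0 and the noncentrality is 0.25 × 20/0.28125 = 17.8. The error variance is then on average 1 + 17.8/19 = 1.94 times too large.

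The documents give no value for π. The values below are assumptions for illustration: 5%, 10% and 20% of the mean (0.125, 0.25, 0.50), with period 2 higher. The last equals the whole planned treatment effect. All figures are one-sided at 0.05.

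| Completers (placebo-first : glutamine-first) | Quantity, within-patient test | π = 5% | π = 10% | π = 20% | Unpaired test |
|---|---|---|---|---|---|
| 10:10 | Bias | 0 | 0 | 0 | 0 |
| 10:10 | Type I error | 4.6% | 3.5% | 1.2% | 5.0% |
| 10:10 | Power at 20% effect | 99.1% | 98.7% | 95.9% | 99.2% |
| 12:8 | Bias | +0.025 | +0.05 | +0.10 | 0 |
| 12:8 | Type I error | 6.9% | 8.0% | 7.6% | 5.0% |
| 8:12 | Bias | −0.025 | −0.05 | −0.10 | 0 |
| 8:12 | Type I error | 2.9% | 1.3% | 0.1% | 5.0% |
| 8:12 | Power at 20% effect | 98.5% | 96.6% | 83.2% | 99.0% |

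If period 2 were lower instead, the 12:8 and 8:12 results would change places.

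**4. How likely imbalance is.** Section 4.3 allows up to 30 recruits "with the goal of 10 individuals completing in each treatment arm". If 20 completers arose at random from 24 (12:12) or 30 (15:15) randomised, the hypergeometric probability of a 12:8 split or worse, in either direction, is 9.3% or 24.5%. Only one direction inflates type I error, so by symmetry that chance is about 5% to 12%. Replacing drop-outs by arm would avoid the imbalance.

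**The case against.** The strongest reply is that 7.6.1 all but determines the right analysis. The table, the one difference per patient, the comparison of sequences and the identity are all correct, and *paired* may mean only that each difference is formed within a patient. Section 7.6.2 refers back to 7.6.1, so a careful analyst would reach the unpaired test in both places. This is largely right, and it is why the point is minor. It does not remove the mismatch: the label is wrong in the only description of the primary test, and its repetition in 7.6.2 reads naturally as a within-patient test.

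It is also fair to say that the harm needs several things together: the within-patient reading, a period effect that the documents do not give and, for inflated type I error, imbalance in one particular direction. At the planned 10:10 that reading is unbiased and errs on the conservative side.

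A reader might infer three stronger things that the documents do not support.
- *That patients would be matched across sequences.* No section proposes this, and it is not a plausible plan.
- *That the sign of the contrast is an error.* A is placebo by the table, so a rise on glutamine makes μ_AB − μ_BA negative. The identity is correct under that labelling.
- *That a one-sided test, and a matching 90% interval, applies throughout.* The one-sided 0.05 level appears only in the ATP/O2 sample-size calculation in 7.3. Section 7.6.1 states an equality null without an alternative, 7.6.2 gives no sidedness, and for lactate and triglycerides 7.2.2 counts lower values as improvement.

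**Conclusion.** The concern holds as a mismatch between the named test and the stated hypothesis. This part rests on the plan's own algebra and randomisation scheme and needs no assumption. The hypothesis itself is sound, the sample size is unaffected, and the power claim survives.

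The practical consequence is conditional. With no period effect the choice between the two tests makes no material difference. The distortions at 12:8 and 8:12 are a sensitivity range under assumed period effects and assumed splits, not a forecast for this trial. A reader might conclude that the primary test as planned has inflated type I error; the documents do not show that. The severity is a minor correction to the stated analysis, worth making because it fixes the test in advance.

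**What to change.** In 7.6.1 and 7.6.2, delete *paired* and state: 'For each patient compute the period 1 minus period 2 difference. Compare the two sequences by an unpaired two-sample t-test (N − 2 degrees of freedom). Estimate glutamine minus placebo as half of (mean difference in the glutamine-first sequence minus mean difference in the placebo-first sequence), with a confidence interval.'

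The cost is a few lines of text and one degree of freedom; no extra patients are needed. With no period effect, power at the planned 20% effect is 99.2% for both tests at 10:10, and 99.0% (unpaired) against 99.2% (within-patient) at 12:8. For a smaller effect of 12%, which is an assumption, the loss at 12:8 is about 2 points (77.0% against 78.6%).

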7.6.2 Secondary Analyses

We will test for difference in each marker of metabolic response profile, oxidative stress, and albuminuria in a similar fashion as above. Similar to above, we will use a two-sample paired t-test testing the difference in means comparing treatment to placebo.

8.0 HUMAN SUBJECTS CONSIDERATIONS

The procedures in the study and model informed consent forms for subjects are to be reviewed by the UW Human Subjects Division (HSD).

Subsequent to initial review and approval, the HSD will review the protocol at least annually. The Investigator will make safety and progress reports to the IRB at least annually, and within three months of study termination or completion. These reports will include the total number of participants enrolled in the study, the number of participants who completed the study, all changes in the research activity, and all unanticipated problems involving risks to human subjects or others.

8.1 Informed Consent

Informed consent will be obtained from each study participant. Consent forms will include the purpose of the study, description of procedures, list of risks and benefits, assurance of confidentiality, assurance of withdrawal without prejudice, description of reimbursement for trial participation (\$125 plus parking and bus fare reimbursement), and a telephone number for answering questions about the research. Patients are also given information regarding their right to privacy for personal health information based on HIPAA regulations, and the procedures for data sharing using de-identified data will be explained. Participants will be provided with a copy of their informed consent forms if they are willing to receive them.

8.2 Risks

The following stated risks will be reflected in the informed consent form and communicated orally to prospective participants at the study site at the time of obtaining consent.

Potential loss of confidentiality is a risk for all study participants, which is address by procedures at the coordinating center described below.

All patient will have a blood draw regularly during the study for a total of four blood draws. The risks of phlebotomy include bleeding/bruising, infection, and discomfort.

For the MRS study, participants may be at risk if they have implanted or non-removable magnetic objects within or on the body, or if loose magnetic items are attracted to the magnet while the subject is near or in the magnet bore. We carefully screen subjects to exclude anyone who has implanted or attached magnetic items. In addition, access to the magnet is strictly controlled and all magnetic objects are kept away from the magnetic field. There is no intravenous contrast used in the MR study.

During the MR study, subjects will have blood pressure cuff inflated to 50 mm Hg over systolic blood pressure. This will remain in place for 12 minutes, increasing risk of thrombosis. To decrease the risk of this, subjects will be screened for past history of deep venous thrombosis, pulmonary embolism, or history of hypercoagulability. Family history for deep venous thrombosis, pulmonary embolism, or history of hypercoagulability will also be obtained.

8.3 Benefits

There may be no direct benefits to participants in this study, however, participants and others may benefit in the future from information learned from this study. Specifically, information learned in this study may lead to the development of a safe and effective intervention that reduce risk of cardiovascular events and risk of disability in persons with CKD.

8.4 Compensation

Participants will be compensated for their time and effort in this study, and/or be reimbursed for travel to study visits and time away from work. Reimbursement amounts will be specified in the study informed consent forms.

8.5 Confidentiality

1. All study-related information will be stored securely at the Kidney Research Institute (KRI) at the University of Washington in Seattle. Access to the KRI is protected by individual unit keys to the elevator, the main institute, and individual offices to prevent tampering or unauthorized access. The use of a Local Area Network (LAN) provides two additional levels of security in the unlikely event of an unauthorized user finding a

machine unattended or unlocked. The LAN restricts access to the Database files via passwords, and the Database itself requires a password before files may be opened.

All study participants are assigned a unique identifier that does not contain identifiable information.

2. All study-related information will be stored securely at the study site. All participant information will be stored in locked file cabinets in areas with access limited to study staff. All laboratory specimens, reports, study data collection, process, and administrative forms will be identified by a coded number to maintain participant confidentiality. All local databases will be secured with password-protected access systems. Forms, lists, logbooks, appointment books, and any other listings that link participant ID numbers to other identifying information will be stored in a separate, locked file in an area with limited access. Participant's study information will not be released without the written permission of the participant.

8.6 Study Discontinuation

The study also may be discontinued at any time by the IRB.

9.0 LABORATORY SPECIMENS AND BIOHAZARD CONTAINMENT

9.1 Local Laboratory Specimens

As described in section 5, the following types of specimens will be collected for testing at the Kidney Research Institute local laboratory. If the participant provides informed consent, his/her specimen will be stored in the KRI repository for additional studies (see section 9.2):

• Fasting blood samples – approximately 23ml of blood per visit at baseline visit and post-intervention visits during each period of the study. During the study a total of approximately 69 mL will be collected per subject.

Local laboratories will perform Chemistries and pregnancy testing.

9.2 Reference Laboratory Specimens

- Blood for metabolomics testing. Aliquots of EDTA preserved blood will be stored at -80°C and sent to Emory University (c/o [name]). All samples will be de-identified.
- Blood for integrated redox state testing will be collected at baseline and post-intervention visits. A 18-, 21-, or 23-guage butterfly needle will be used to draw up 3mL of blood into a 5ml syringe. Enough blood will be immediately placed in a microcentrifuge tube containing 150μL of preservative solution to attain a total volume of 1.5mL. These samples will be frozen at -80°C and sent in bulk to Emory University (c/o [name]. See reference for more

- details: Jones DP. Measuring the poise of thiol/disulfide couples in vivo. *Free Radical Biology and Medicine*. 47(2009):1329-38.)
- Blood for F2-isofuran and F2-isoprostane assays will be frozen at -80°C and sent in bulk to Vanderbilt University (c/o [name]).

Purpose	Sample Type	Maximum Amount per Sample	Number Samples	Total Amount
Baseline/Post-intervention	Blood	-	-	23/46 mL
Venous lactate (3 mL grey top)	Blood	3 mL	3	9 mL
Renal Panel, triglycerides (green top)	Blood	4 mL	3	12 mL
F2 isoprostanes/isofurans, metabolomics (EDTA)	Blood	10 mL	3	30 mL
Redox testing (N & S tubes)	Blood	3 mL	3	9 mL
CBC (3ml lavender top)	Blood	3 mL	3	9 mL
Total blood collected during study			\rightarrow	69 mL
Baseline/Post-intervention	Urine	-	-	n/a
Urine Creatinine (24 hour)	Urine	n/a	2	n/a
Urine albumin (24 hour)	Urine	n/a	2	n/a
Urine Urea Nitrogen (24 hour)	Urine	n/a	2	n/a
Urine pregnancy	Urine	10 mL	1	10 mL

